**Figure 2:** Hypothetical example of study data showing random clinic intercepts and intervention effects. Each line shows the expected profile for a specific clinic. Here clinic 1 initiates intervention at quarter=2 while clinic 2 initiates at quarter=4.

**Key Model Parameters:** The primary parameter of interest is  $\lambda_0$ , which represents the average effect of the intervention adjusting for temporal trends ( $Time_t$ ), clinic characteristics ( $Site_k$ ,  $Size_k$ ), and individual covariates ( $Age_{ijk}$ ,  $Modality_{ijk}$ ). In order to interpret the random effects structure we focus on clinic level means removing covariate effects where we have: adjusted mean at clinic  $k$  for times prior to intervention =  $\beta_0 + b_{k,0}$ ; and the adjusted mean at clinic  $k$  for times after start of the intervention =  $\beta_0 + b_{k,0} + \lambda_0 + b_{k,1}$ . For clinic-specific means we average over both providers ( $a_{jk,0}$ ) and patients ( $e_{ijk}$ ). Using this representation

we interpret  $\beta_0$  as the pre-intervention adjusted overall mean outcome averaging across all clinics, and  $b_{k,0}$  is the difference between that adjusted overall mean and the pre-intervention (baseline) mean for clinic  $k$ . The variance,  $var(b_{k,0})$ , is a measure of the variation in the baseline mean outcome across clinics. The change in the adjusted mean outcome for clinic  $k$  is given by: (post-intervention adjusted mean) – (pre-intervention adjusted mean) =  $(\beta_0 + b_{k,0} + \lambda_0 + b_{k,1}) - (\beta_0 + b_{k,0}) = \lambda_0 + b_{k,1}$ . Here  $\lambda_0$  represents the average intervention effect across all clinics and  $b_{k,1}$  represents the difference between that average intervention effect and the intervention effect for clinic  $k$ . The variance,  $var(b_{k,1})$ , is a measure of the variation in the change associated with intervention across clinics, or a measure of the heterogeneity of the intervention effect.

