Our primary regression model acknowledges the fundamental multilevel structure of individual-level data collected in health care systems with patients nested within providers, and providers nested within clinics. Although, the basic intervention contrast is the pre-post change associated with the initiation of intervention for each clinic, we do not propose using clinic-level summary measures for inference since the weighting of both patients and providers is not simple when heterogeneity of cluster sizes exists (e.g. PCPs per clinic, and patients per PCP). A proper multilevel model allows for optimal weighting based on the estimated variance components

Lumbar Imaging Reporting with Epidemiology (LIRE)  
STATISTICAL ANALYSIS PLAN

(e.g. Gauss-Markov) and yields both an efficient summary of the overall intervention effect, as well an estimate of the variability in the magnitude of effect across clinics. However, we will not rely on the covariance model being correct for statistical inference and will use a robust (empirical) standard error. With greater than 100 total clusters (clinics) we expect valid inference and proper test size and do not anticipate needing to perform any correction such as the jackknife (recommended when the number of clusters is small).

In our analysis we effectively assume that individual patients are nested within a single provider. However, in practice a patient may change providers during the follow-up year over which the primary outcome is captured. However, our basic mixed model covariance structure will simply use the assigned primary provider at the index imaging time. Therefore, we do not rely on model-based standard errors since the covariance structure may not match the true within-clinic covariance structure. We will use robust standard errors clustering at the clinic level, and therefore our analysis is valid even if there are changes in patient provider leading to an incorrectly specified covariance structure. Robust standard errors remain valid when a covariance model is not correctly specified. Furthermore, key secondary analysis of the primary outcome will directly use GEE and only cluster at the clinic level and provider level linkages are not used (nor needed) for simple GEE analysis.

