**Secondary Analyses of Primary Outcome:** We will conduct additional secondary analyses that evaluate the sensitivity of the multilevel model to the assumed basic random effects structure. We have included in the primary model multilevel random intercepts and a random effect for the clinic-level intervention. However, we will expand the random effects structure to also permit random slopes on time for both clinics and providers. Given the relatively short duration of follow-up with only six (6) total measurement times we do not expect strong heterogeneity across providers or clinics in cluster-specific temporal trends. Figure 2 shows an example of hypothetical data series for two clinics (assuming aggregation of providers to a clinic summary) and illustrates both the staggering of the crossover time and the potential to observe clinic-specific intervention effects. This figure also illustrates the fact that separating random effects of time (linear) from random effects of intervention would be difficult since time and intervention status are correlated give the unidirectional crossover from control to intervention. In addition, we will use GEE as a covariance model robust inference method and therefore can produce valid point estimates and confidence intervals without relying on correct covariance specification. Details of model choice and comparison of alternative models for longitudinal cluster level crossover trials is presented in French and [name] (2008) and comparison of alternative approaches is recommended.

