To our knowledge, off-the-shelf calculators do not exist that would adequately characterize statistical power for a stepped wedge cluster randomized trial with a varying number of sampling units between clusters. We therefore utilized simulation methods to generate and analyze data that closely mimics the design characteristics we anticipate for this study. With a simulation approach, we were able to include estimates of both patient and clinic-level variability and implement the proposed primary analysis methods: random intercept linear mixed effects models for RVU outcomes; and generalized linear mixed models for opioid prescription rates. All simulations

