## Lumbar Imaging Reporting with Epidemiology (LIRE) STATISTICAL ANALYSIS PLAN

were conducted using R (version 3.0.1) with the *lmer* and *glmmPQL* functions implementing mixed model estimation.

**Power for Primary Outcome:** In the BOLD Registry we identified 639 patients in the Kaiser Permanente and Henry Ford health systems that had a qualifying lumbar image within 6 weeks of a PCP visit, the majority (74%) of which occurred within 7 days. As one would expect with a measure of health care utilization intensity, patient-level RVUs are positively skewed. In our simulations and in the future analysis of study data, we therefore utilize an approximately normalizing transformation of  $\log(\text{RVU} + 1)$  but will make interpretations regarding effect size back on the original RVU scale.

With log-transformed BOLD Registry RVU data, we fit a linear mixed effects model adjusting for image type (advanced vs. plain film) and study recruitment site and estimated the variance components for clinic (0.026) and the residual error term (1.230). The observed intra-class correlation coefficient (ICC) across clinics was 0.013 (95% CI: 0.000 to 0.046). In this subset of BOLD data, the number of PCPs with multiple patients was too few to inform the PCP-level variance component and it is therefore conservatively included in the error term variance for power simulations.

The numbers of clinics and primary care providers were considered fixed for each simulation and we assumed that each provider would provide data for all study time periods. For a range of potential RVU effect sizes, we generated 1,000 simulated data sets and performed mixed model estimation with each data set. In Figure 2, we show statistical power for the primary outcome measure of PCP spine-related RVU under the proposed study design. The study has greater than 90% power to detect reductions in the median spine-related RVU of 5.0% or larger. For a patient receiving a lumbar CT, a 5% reduction in spine RVU translates into one fewer additional lumbar CT scan on average compared to a patient unexposed to the LIRE intervention.

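### The stated ICC of 0.013 does not follow from the stated variance components (0.0207), and both power figures come from random-intercept models although the planned models also contain a random clinic-level intervention effect

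*SAP*

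**What the plan says.** **Inputs.** Under Power for Primary Outcome, the SAP fits a mixed model to log-transformed BOLD data and reports that it "estimated the variance components for clinic (0.026) and the residual error term (1.230"). It continues: "The observed intra-class correlation coefficient (ICC) across clinics was 0.013 (95% CI: 0.000 to 0.046"). PCP-level variance could not be estimated separately and is "conservatively included in the error term variance for power simulations".

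**Simulation model.** Power Calculations says the simulations could "implement the proposed primary analysis methods: random intercept linear mixed effects models for RVU outcomes", with generalized linear mixed models for opioids. Power for Secondary Outcome says the opioid data sets were also evaluated with random intercepts.

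**Claims.** For the primary outcome: "The study has greater than 90% power to detect reductions in the median spine-related RVU of 5.0% or larger". For opioids, 88.9% power for a 7.5% relative reduction from 22%.

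**Planned models.** Secondary Analyses of Primary Outcome says: "We have included in the primary model multilevel random intercepts and a random effect for the clinic-level intervention". The equations under Primary Analysis and Secondary Outcome Analysis both contain this term, b(k,1) × Status. Protocol 5.7 (Aim 1a) likewise plans a random effect for the intervention. Key Model Parameters explains that the variance of b(k,1) "is a measure of the variation in the change associated with intervention across clinics" and that the model will give "an estimate of the variability in the magnitude of effect across clinics".

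**The concern.** There are two separate problems in the same few paragraphs.

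First, the ICC and the variance components stand in adjacent sentences and disagree, so a reader cannot tell which is the design input.

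Second, the simulated model is called the proposed primary analysis but omits one of its random effects. A random-intercept simulation sets the between-clinic variance of the intervention effect to zero. If the effect does vary, the average effect is estimated less precisely and power falls. The SAP expects to measure this variation, yet its power text assigns it no value. That text also does not mention the clinic-robust standard error, or the three-month washout to which Protocol 5.7 commits (the SAP's General Analytic Strategy only considers it).

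At stake is how a null or small result is read. Someone relying on the claim of more than 90% power for a 5% reduction should know that it is conditional.

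**Working it through.** **1. ICC.** Clinic variance / (clinic + residual variance) = 0.026 / (0.026 + 1.230) = 0.0207. Rounding of the inputs allows only 0.0203 to 0.0211. Other readings do not give 0.013: residual taken as an SD, 0.0169; both taken as SDs, 0.0004; clinic/residual, 0.0211. With residual 1.230, an ICC of 0.013 needs a clinic variance of 0.013 × 1.230/0.987 = 0.0162. PCP variance does not explain the gap, because the SAP places it inside the 1.230.

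**2. Inputs for power.**
- From the documents: effect ln(0.95) = −0.0513; the variance components above; Table 1 of the SAP (110 clinics, 1,824 PCPs); five waves; about 100,000 patients (Protocol, human subjects section); 98 clinics (SAP Revisions).
- Assumed: two-sided alpha 0.05; equal patients per PCP and quarter; clinic sizes interpolated within the Table 1 bounds; washout equal to the quarter before crossover; for 98 clinics, two small clinics plus ten others dropped at random, since the SAP does not identify them.
- Method: generalized least squares on clinic-by-quarter cells with linear time, site and size, over 30 random allocations. Power = Φ(0.0513/SE − 1.960).

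**3. The SAP's figures under its own model.** With random intercepts and no washout, SE = 0.0122 and power = Φ(4.20 − 1.96) = 98.8%, for 110 or 98 clinics. This agrees with the claim of more than 90%. Using ICC 0.013 gives 98.9%. For opioids, a linear approximation on the probability scale (clinic SD from the SAP's Beta(6,20), 110 clinics, half of the six-month period before crossover removed) gives 89.3% against the stated 88.9%.

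**4. Adding the planned random intervention effect.** Let τ be the SD of b(k,1) on the log scale. With 98 clinics, washout and 100,000 patients (power and detectable reduction from unrounded SEs):

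| τ | SE | Power at 5% reduction | Reduction detectable with 90% power |
|---|---|---|---|
| 0 | 0.0139 | 95.9% | 4.4% |
| 0.05 | 0.0154 | 91.6% | 4.9% |
| 0.075 | 0.0167 | 86.7% | 5.3% |
| 0.10 | 0.0183 | 80.2% | 5.7% |

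Hand check: the estimator's weights on the clinic effects sum to 1, so the added variance is at least τ²/98. At τ = 0.10, SE is at least √(0.0139² + 0.01/98) = 0.0172, and power is at most Φ(0.0513/0.0172 − 1.96), about 85%. The table's 80% is lower because clinics differ in size.

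Power drops below 90% at τ of about 0.059, slightly above the mean effect. At that value Φ(−0.0513/0.059) = 19% of clinics would see an increase.

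**5. Sensitivity of that threshold.**
- Patients: 0.024 at 80,000 and 0.077 at 120,000. Without washout: 0.063, 0.084 and 0.096 at 80,000, 100,000 and 120,000.
- 110 clinics with washout: 0.063.
- If 1–10% of the 1.230 is PCP variance (assumed): 0.060–0.069.
- If patients fall in proportion to clinics (100,000 × 98/110 = 89,091), power at τ = 0, 0.05, 0.075 and 0.10 is 93.8%, 89.0%, 83.8% and 77.4%.
- Adding the site-by-time terms from the SAP Revisions: 95.9%, 91.3%, 85.8% and 78.8%.
- Robust versus model-based SE (2,000 simulated trials at each of τ = 0, 0.05 and 0.10): a difference under 0.5 point.
- A different layout (110 clinics, strata midpoints scaled to site totals, half of the preceding period removed): 96.3%, 92.8% and 82.8% at τ = 0, 0.05 and 0.10. ICC 0.013 changes the first to 96.6%.

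**6. Opioids.** logit(0.22) − logit(0.2035) = 0.0989. A power of 88.9% implies SE = 0.0989/(1.960 + 1.221) = 0.0311. Adding at least τ²/110, with τ now on the logit scale, gives power of at most 86.0%, 82.4% and 77.4% at τ = 0.10, 0.15 and 0.20.

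**The case against.** Four points deserve weight.

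- **The label is largely there.** The SAP names random intercepts in both power passages. That is so, but it also equates them with the proposed primary methods, which the model equations contradict. A reader is told that the two are the same.
- **The primary claim is not refuted.** It survives 98 clinics, washout and τ = 0.05 together, at about 100,000 patients. BOLD contained no LIRE intervention, so it could not have supplied τ. This stands, and is why the result is a sensitivity range only.
- **Precision covariates are not credited.** The 1.230 was adjusted only for image type and site, whereas the planned and amended models add age, gender and Charlson category. If these explain 5%, 10% or 20% of residual variance (assumed), the threshold rises from 0.059 to 0.065, 0.070 or 0.081. These values lie inside the range already shown. For opioids, the amended model adds prior opioid status, so the upper bounds in step 6 apply only to the model as written in the SAP body.
- **The rerun is retrospective.** The revisions concern models used for the manuscript; enrolment cannot change, and the achieved confidence interval will show precision directly. That limits the benefit, but a stated design claim should still match the stated analysis.

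Nor does silence about washout prove that the simulation omitted it. The robust standard error is no answer to the main point: it protects the validity of the test but carries the extra between-clinic variance. In the alternative layout of step 5, a random-intercept fit with robust SEs has power 91.9% at τ = 0.05 and 75.6% at τ = 0.10.

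**Conclusion.** Both parts hold. The ICC as printed is inconsistent with its own components: 0.0207 against 0.013. Since 0.0207 lies within the printed interval and power hardly moves, this is a reporting correction, or else an unnamed estimator.

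The power figures are supported only for models simpler than those planned. For the primary outcome, the claim of more than 90% fails once τ exceeds roughly 0.06 under the central assumptions; the threshold runs from 0.024 to 0.096 over 80,000 to 120,000 patients, with or without washout. The direction is secure. The exact threshold is not, because τ and the patients per PCP and period used in the SAP's simulation are not stated, and the power figure could not be seen. It should be corrected, but it does not show that the trial is underpowered.

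**What to change.** 1. Correct the ICC or the variance component, or name the estimator that produced 0.013.
2. Rerun the primary simulation with the planned model: a random intervention effect over a stated range of SDs, clinic-robust standard errors, washout, stated patients per PCP and period, and 98 clinics. Report power, or the detectable reduction, as conditional on the SD.
3. At minimum, remove the statement that the simulated models are the proposed primary methods, and attach a random-intercept-only label to the primary and opioid figures themselves.

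The cost is one corrected number and a rerun of existing R code, or only a label. No patients are added and the design does not change. The stated power becomes conditional and somewhat less favourable.

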**Power for Secondary Outcome:** Using the updated clinic and provider listing, we repeated the UH2 power analyses for a reduction in subsequent opioid prescriptions. We again used an average baseline opioid prescription rate of 22%, suggested from the pilot manuscript to anchor the effect size of percent reduction in the baseline rate. A clinic-specific baseline opioid prescription rate was drawn from a Beta( $\alpha=6$ ,  $\beta=20$ ) distribution; we used this rate to draw a baseline opioid prescription rate random effect for each primary care provider using a clinic-specific log-normal distribution. We generated 1,000 simulated data sets using the effect size of a 7.5% reduction in the opioid reported in our UH2 application and evaluated each using a GLMM assuming random intercepts. With 110 clinics randomized, the study remains well powered (88.9% power) to detect a reduction in the rate of opioid prescriptions of 7.5% or larger (e.g. 22% down to 20.4%).

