**Lumbar Imaging with Reporting of Epidemiology (LIRE) Statistical Analysis Plan Revisions**

The following table includes amendments to our statistical analysis plan (SAP) that we included in statistical models for the manuscript but that we did not specify in our original SAP.

Amendments to Statistical Analysis Plan (SAP)	
Number of clinics	

 
• 110 to 98 clinics
 
	When we wrote the SAP we estimated that we would have 110 clinics participating in the trial. We dropped ten clinics prior to randomization for logistical reasons. We dropped two additional small clinics just after randomization and before the first data submission: one had closed and the other had been subsumed in another clinic.
Covariates	We made all decisions regarding covariates before we began the statistical analysis.
Covariates added	Rationale

 
• Site by time interactions
 
	Allow for differential time trends by site

 
• Gender
 
	Allow for outcome differences by gender (precision)

 
• Charlson Comorbidity Index category
 
	Comorbidity measures are associated with outcomes. We sought greater precision by including this general measure of health.

 
• Prior opioid status (opioid models only)
 
	Allow for differences in outcome between those without and those with prior opioid prescriptions (precision)
Covariates transformed	

 
• Time
 
	The SAP and protocol paper indicated that we would model time linearly as 6-month time period (t = 0, 1, 2, 3, 4, 5). Upon further thought, we decided that a more granular measure (i.e. day) would be more appropriate.

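### The opioid power of 88.9% is tied to a stated 22% baseline, but the stated Beta(6, 20) clinic distribution averages 23.1%, and the figure was not restated for 98 clinics

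*SAP*

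**What the plan says.** The SAP, under Power for Secondary Outcome, states: "We again used an average baseline opioid prescription rate of 22" per cent. It takes that rate from the pilot publication and uses it "to anchor the effect size of percent reduction in the baseline rate".

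The simulation is then described in two steps. First, "A clinic-specific baseline opioid prescription rate was drawn from a Beta" distribution with alpha = 6 and beta = 20. Second, that clinic rate is used to draw a "baseline opioid prescription rate random effect for each primary care provider using a clinic-specific log-normal distribution"; the parameters of the log-normal are not given.

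On the effect and the runs: "We generated 1,000 simulated data sets using the effect size of a 7.5% reduction". The result reads "With 110 clinics randomized, the study remains well powered (88.9% power") for a reduction of "7.5% or larger (e.g. 22% down to 20.4" per cent).

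The table of SAP revisions, under Number of clinics, records "110 to 98 clinics". Ten clinics were dropped before randomization for logistical reasons and two small ones just after it. No power figure is given for 98 clinics.

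**The concern.** Two statements in one paragraph do not agree. An average of 22% is claimed, but the distribution named for the clinic rates has a different mean. At a fixed relative reduction, a higher baseline gives a larger absolute difference and a stronger signal. A simulation at 23.1% therefore returns somewhat more power than one at 22%. A reader cannot tell which baseline the 88.9% describes.

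The second element is separate. When the clinic count changed from 128 to 110, the SAP repeated this power analysis on the updated clinic and provider list. No such update accompanies the later change to 98.

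What is at stake is the accuracy of a planning statement for a secondary outcome that the SAP calls important. The design and the analysis model are not affected.

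**Working it through.** **Reproducing 88.9%.** This cannot be done from the documents. Patients per PCP per period, the log-normal parameters, the time structure in the simulation and alpha are not stated. An approximate stepped-wedge power formula on the logit scale shows how much the missing inputs matter. It used 110 clinics at each site's mean PCP count from SAP Table 1, six periods, five waves, a clinic variance implied by Beta(6, 20), and an assumed two-sided alpha of 0.05. With a time term and a 23.1% baseline, power is about 25% at 1 patient per PCP-period, 79% at 5, 88.9% at about 6.7 (about 73,000 patients) and 97% at 10. Without a time term, 88.9% is reached at about 2.7 (about 29,000 patients). What follows therefore scales from the stated 88.9% and does not recompute it.

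**Step 1: the mean of the stated distribution.** Mean = alpha/(alpha + beta) = 6/(6 + 20) = 0.2308. The median is 0.224 and the mode 0.208.

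**Step 2: the effect at each baseline.**
- At 22%: 0.925 × 22 = 20.35%, a difference of 1.65 points.
- At 23.08%: 0.925 × 23.08 = 21.35%, a difference of 1.73 points.

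**Step 3: relative signal.** With q = 0.925p, signal = (p − q)/√{[p(1 − p) + q(1 − q)]/2}.
- At 22%: 0.0165/√0.16684 = 0.0404.
- At 23.08%: 0.01731/√0.17270 = 0.0416.
- The ratio before rounding is 0.970. The log-odds version gives the same ratio.

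**Step 4: scaling from 88.9%.** The noncentrality for 88.9% power is 1.960 + 1.221 = 3.181. For 98 clinics of average size it is multiplied by √(98/110) = 0.944.

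| Scenario | Noncentrality | Power |
|---|---|---|
| 23.1% mean, 110 clinics (taken as given) | 3.181 | 88.9% |
| 22% mean, 110 clinics | 3.181 × 0.970 = 3.086 | 87.0% |
| 23.1% mean, 98 clinics | 3.181 × 0.944 = 3.003 | 85.1% |
| 22% mean, 98 clinics | 3.086 × 0.944 = 2.912 | 83.0% |

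**Step 5: simulation error.** With 1,000 runs, SE = √(0.889 × 0.111/1000) = 0.0099, or about 1 point. The baseline shift of 1.9 points is about two such errors.

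**Step 6: sensitivity to which clinics were lost.** The revisions call only two of the twelve small; the sizes of the other ten are not given. In the approximate model, at the 23.1% baseline, losing all twelve from the site with the fewest PCPs per clinic (Henry Ford, 230/26 = 8.8) leaves about 87%. Losing them from the site with the most (Kaiser, 865/20 = 43.3) leaves about 77%.

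**The case against.** The strongest reply is that the simulated average is not known to be 23.1%, because patients are not generated directly from the Beta. Provider rates come from a log-normal with unstated parameters. The Beta median, 22.4%, is also close to 22%, and the 22% to 20.4% example is correct arithmetic and marked as an example. This stands only in part. If the log-normal is centred on the clinic rate by its mean, the average stays at 23.1%; if by its median, the average rises. Bringing it down to 22% would need a downward shift that the SAP does not describe, and the SAP says average, not median.

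The reply is stronger on size. A shift of 1.9 points is about as large as the simulation noise.

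On the clinics, the reply is right that no error was made. The figure is openly conditional on 110, and the revisions disclose the change and explain it. What remains is that the power was not restated.

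A reader might go further and infer that the stated power is too high for the trial as run, or that the trial was underpowered for opioids. The documents do not support that. The 88.9% cannot be reproduced, and the sizes of ten dropped clinics are unknown. The revisions also add prior opioid status and other covariates for precision, which the described simulation does not include. The protocol, just before section 7.2, anticipates about 100,000 patients. In the approximate model with a time term and 110 clinics, that number gives about 95% at a 22% baseline and 96% at 23.1%.

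**Conclusion.** The inconsistency is real and small. The stated clinic distribution averages 23.1%, so 88.9% does not describe the 22% to 20.4% scenario attached to it. Taking 88.9% as correct for a 23.1% mean, with two-sided alpha 0.05 assumed, the 22% scenario with 110 clinics has about 87% power.

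The clinic count makes the figure outdated, not wrong. If average-size clinics were lost and nothing else changed, power is about 85% at the 23.1% mean and about 83% at 22%. Both exceed 80%. Neither can be quoted as the power of the trial as run, because the dropped clinics' sizes, the patient numbers and the added covariates could move it down or up. This is a minor correction to the documentation.

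**What to change.** Re-run the simulation with a Beta distribution of mean 0.22 and the same total. For example, Beta(5.72, 20.28) has 0.22 × 26 = 5.72 and 26 − 5.72 = 20.28. Use the actual list of 98 clinics and their PCPs, and report whatever power results without fixing a target figure in advance. State the missing inputs alongside it: patients per PCP per period, the log-normal parameters, the time term and alpha.

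At minimum, without a re-run, give the clinic-level baseline mean as 23.1%, change the example to 23.1% down to 21.3%, and label 88.9% as the planning figure for 110 clinics.

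The cost is one simulation run, or an edit of a few words, and probably a slightly less favourable number if the other inputs are kept. The design and the analysis do not change.
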